Main symptoms of Behcet's disease: presence or absence of eye symptoms	If there is a check mark in “1,2,3” in “eye symptoms” at the start of administration of this drug in survey sheet with the date before the start date of the initial administration of this drug, eye symptoms is deemed to be present, and in any other situations, it is deemed to be absent.
Main symptoms of Behcet's disease: presence or absence of ulcer of vulva	If there is a check mark in “1,2,3” in “ulcer of vulva” at the start of administration of this drug in survey sheet with the date before the start date of the initial administration of this drug, ulcer of vulva is deemed to be present, and in any other situations, it is deemed to be absent.
Main symptoms of Behcet's disease: presence or absence of arthritis without deformity or rigidity	If there is a check mark in “1,2,3” in “arthritis without deformity” at the start of administration of this drug in survey sheet with the date before the start date of the initial administration of this drug, arthritis without deformity is deemed to be present, and in any other situations, it is deemed to be absent.
Accessory symptoms of Behcet's disease: presence or absence of	If there is a check mark in “epididymitis” at the start of administration of this drug in survey sheet with the date before the start date of the initial administration of this drug,

Name of data	Derivation and calculation method
epididymitis	epididymitis is deemed to be present, and in any other situations, it is deemed to be absent.
Accessory symptoms of Behcet's disease: presence or absence of vascular lesion	If there is a check mark in “vascular lesion” at the start of administration of this drug in survey sheet with the date before the start date of the initial administration of this drug, vascular lesion is deemed to be present, and in any other situations, it is deemed to be absent.
Accessory symptoms of Behcet's disease: presence or absence of moderate or higher degree central nervous lesion	If there is a check mark in “moderate or higher degree central nervous lesion” at the start of administration of this drug in survey sheet with the date before the start date of the initial administration of this drug, moderate or higher degree central nervous lesion is deemed to be present, and in any other situations, it is deemed to be absent.

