BMI	Younger than 18.5 years, 18.5 years or older and younger than 25 years, 25 years or older and younger than 30 years, 30 years or older, unknown
Smoking habit	Absent, present, unknown, not described
Disease duration (years)	Shorter than 2, 2 or longer and shorter than 5, 5 or longer and shorter than 10, 10 or longer, unknown/not described
Reasons for use	Gastro-intestinal Behcet disease, other conditions, unknown, not described
Diagnostic classifications of Behcet disease	Complete type, incomplete type, suspected, others, unknown/not described
Main symptoms of Behcet disease	Recurrent oral mucosa aphthous ulcer, cutaneous symptoms, eye symptoms, ulcer of vulva
Evaluation of main symptoms of Bechet disease	0,1,2,3 Recurrent oral mucosa aphthous ulcer Cutaneous symptoms (erythema nodosum, subcutaneous phlebitis, folliculitis-like skin eruption, acne-like skin eruption) Ulcer of vulva Eye symptoms
Presence or absence of eye symptoms of	There is no symptom: Point for evaluation of main symptoms of Bechet disease is 0

data	Method of dividing hierarchy
Bechet disease	There are any symptoms: Points for evaluation of main symptoms of Bechet disease are 1,2,3 Unknown/not described: Other than above situations
Accessory symptoms of Bechet disease	Arthritis without deformity or rigidity, epididymitis, gastrointestinal lesions characterized by ulcer of ileocecum, vascular lesion, moderate or higher degree central nervous lesion
Presence or absence of accessory symptoms of Bechet disease	There are any symptoms: there are check marks in boxes for each accessory symptom There is no symptom: Other than above
History of allergy	Absent, present, unknown, not described
Tuberculin test or IGRA test	Not implemented, implemented, unknown, not described
HBs antigen	Not implemented, implemented, unknown, not described
HBs antibody	Not implemented, implemented, unknown, not described
HBc antibody	Not implemented, implemented, unknown, not described
HBV-DNA quantitative	Not implemented, implemented, unknown, not described
Complications	Absent, present, unknown, not described
Detailed classification of complications	Liver disorder, renal disorder, circulatory disorder, blood disorder, respiratory disorder, others
Other classifications of complications	Diabetes mellitus, gastrointestinal disorder, osteoporosis, malignant tumour, collagen disorder, others
Medical history	Absent, present, unknown, not described

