## “1.12.1 Distribution of patient characteristics”

Patients included in analysis: Patients included in safety analysis, patients included in efficacy analysis, patients whose survey sheet data was fixed

Objective of analysis: Distribution of patient characteristics is shown

Analysis items: The number of patients included in analysis should be calculated.

The number of patients according to following classifications defined in “11 method of dividing hierarchy of data” and rate of these patients to those included in analysis should be calculated.

Sex, pregnancy/lactation, race, age (years), body weight (kg), body height (cm), BMI (kg/m^2), smoking habit, disease duration (years), reasons for use, diagnostic classifications of Behcet disease, main symptoms of Behcet disease, accessory symptoms of Behcet disease, allergy history, tests for tuberculosis, test for hepatitis B, complications, detailed classifications of complications (liver disorder, renal disorder), medical history, previously used drug/previous treatment, classifications of biological preparations as previously used drug/previous treatment, classifications of drugs other than biological preparations as previously used drug/previous treatment, concomitant drugs, detailed classifications of concomitant drugs, combination therapy, detailed classifications of combination therapy, endoscopy, detailed classifications of endoscopy

In addition, summary statistics should be calculated for following items.

Age (years), body weight (kg), body height (cm), BMI (kg/m^2), disease duration (years)

Notes: Rate of pregnancy/lactation should be calculated as that to female patients.

In addition, breakdown of each item should be represent the rate of patients to the aggregated number of patients corresponding to the item at one-step higher hierarchical level.

(Example: Rate of patients according to detailed classifications of complication to all patients who have complications should be calculated)

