**“2.9 Incidence of adverse reactions (serious adverse reaction and adverse reaction) by patient characteristics”**

Patients included in analysis: Patients included in safety analysis

Objective of analysis: Incidence of adverse reactions should be shown by patient characteristics and factor analysis should be conducted.

Analysis items: In patients in whom adverse reactions occurred in the period subject to safety analysis, the number of all the patients, the number of patients with serious adverse reactions, and rate of these patients to those included in analysis, the number of the patients with adverse reactions and rate of these patients to those included in analysis, and test provided for the adverse reactions (Fisher’s exact test for nominal scale factors, and Mann-Whitney u test for ordinal scale factors) should be calculated by following patient characteristics:

Notes: Patient characteristics are as follows: Age (years), sex, disease duration (years), complication, hepatic function disorder as complication, renal impairment as complication, medical history, allergy history, smoking habit, self-administration as administration status of this drug, previously used drug/previous treatment, biological preparation adalimumab as previously used drug, biological preparation infliximab as previously used drug, steroid as previously used drug, immunomodulative drug as previously used drug, immunosuppressive drug as previously used drug, oral adrenocortical steroid as concomitant drug, oral mucosa recurrent aphthous ulcer as main symptoms of Behcet disease other than gastrointestinal symptoms, cutaneous symptoms as main symptoms of Behcet disease other than gastrointestinal symptoms, eye symptoms as main symptoms of Behcet disease other than gastrointestinal symptoms, ulcer of vulva as main symptoms of Behcet disease other than gastrointestinal symptoms, arthritis without deformity or rigidity as accessory symptoms of Behcet disease other than gastrointestinal symptoms, epididymitis as accessory symptoms of Behcet disease other than gastrointestinal symptoms, vascular lesion as accessory symptoms of Behcet disease other than gastrointestinal symptoms, moderate or higher degree central nervous lesion as accessory symptoms of Behcet disease other than gastrointestinal symptoms, diagnostic classification of Behcet disease, days until the last date of the administration, and mean daily dose.

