#### “3.4 Aggregation of efficacy by patient characteristics”

Patients included in analysis: Patients included in efficacy analysis

Objective of analysis: As primary survey item, efficacy ratio in level of improvement at the last follow-up for factor analysis.

Analysis items: The number of patients included, the number of responding patients regarding level of overall improvement (significant improvement and improvement) and rate of these patients to those included in analysis, the number of patients who showed ineffectiveness in level of overall improvement and rate of these patients to those included in analysis, and test provided for effectiveness (Fisher’s exact test for nominal scale factors, and Mann-Whitney u test for ordinal scale factors) were calculated by following patient characteristics.

Notes: Patient characteristics are as follows:

Age (years), sex, disease duration (years), complication, hepatic function disorder as complication, renal impairment as complication, medical history, allergy history, smoking habit, self-administration as administration status of this drug, previously used drug/previous treatment, biological preparation adalimumab as previously used drug, biological preparation infliximab as previously used drug, steroid as previously used drug, immunomodulative drug as previously used drug, immunosuppressive drug as

previously used drug, oral adrenocortical steroid as concomitant drug, oral mucosa recurrent aphthous ulcer as main symptoms of Behcet disease other than gastrointestinal symptoms, cutaneous symptoms as main symptoms of Behcet disease other than gastrointestinal symptoms, eye symptoms as main symptoms of Behcet disease other than gastrointestinal symptoms, ulcer of vulva as main symptoms of Behcet disease other than gastrointestinal symptoms, arthritis without deformity or rigidity as accessory symptoms of Behcet disease other than gastrointestinal symptoms, epididymitis as accessory symptoms of Behcet disease other than gastrointestinal symptoms, vascular lesion as accessory symptoms of Behcet disease other than gastrointestinal symptoms, moderate or higher degree central nervous lesion as accessory symptoms of Behcet disease other than gastrointestinal symptoms, diagnostic classification of Behcet disease, days until the last date of the administration, and mean daily dose.

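### Tables 2.9 and 3.4 test epididymitis with every woman counted as 'absent', which builds sex into the comparison; the effect is probably modest, and a male-only filter removes it

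*SAP*

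**What the plan says.** SAP section 10.1 derives the baseline epididymitis item from a check mark on the survey sheet. With the mark, "epididymitis is deemed to be present, and in any other situations, it is deemed to be absent". Section 11 gives accessory symptoms the same two classes, with a residual one: "There is no symptom: Other than above". Neither place has a class for patients in whom the condition cannot occur.

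Table 2.9 in section 13.2 sets its population as "Patients included in analysis: Patients included in safety analysis", lists "epididymitis as accessory symptoms of Behcet disease other than gastrointestinal symptoms" among the characteristics, and prescribes "Fisher’s exact test for nominal scale factors". Table 3.4 in section 13.3 repeats the factor list for response: "Patients included in analysis: Patients included in efficacy analysis", with "test provided for effectiveness (Fisher’s exact test for nominal scale factors". Sex is a separate one-way factor in both lists. Neither table has a stratified or adjusted analysis.

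Section 9.5 removes only unknown or undescribed values from tests, so women classed as absent stay in. For another sex-specific item the plan does restrict the denominator. The notes to Table 1.12.1 state: "Rate of pregnancy/lactation should be calculated as that to female patients".

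**The concern.** Epididymitis occurs only in men. Under these rules the present group is entirely male, and the absent group is a mixture of unaffected men and every woman in the set. The factor is therefore tied to sex by construction. Women tell us nothing about whether epididymitis is associated with adverse reactions or response, yet they may be about half of the comparison group.

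Section 4.1 names factors contributing to safety and efficacy as an objective, and Tables 2.9 and 3.4 are the factor analyses that serve it. If women have more (or fewer) reactions than men, part of that difference would appear on the epididymitis line. A significant result in Table 2.9 also triggers a further breakdown by seriousness for that characteristic, and section 9.5 applies no multiplicity control.

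**Working it through.** **No figure to reproduce.** Section 4.3 leaves the number of patients undecided, and the SAP gives no sex split, no prevalence of epididymitis and no reaction rates. All inputs below are assumptions. Only the two-sided 5% level comes from the plan (section 9.6).

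**Step 1: expected gap with no true effect.** Let A be the unaffected men, F the women, p_m the reaction rate in men (the same with or without epididymitis) and p_f the rate in women.

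- Present group: p_m
- Absent group as planned: (A × p_m + F × p_f) / (A + F)
- Gap, absent minus present: F / (A + F) × (p_f − p_m)

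The gap is zero when p_f = p_m. For a rare condition it is close to the female share times the sex difference.

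Assume 400 patients, half of them men, and 10% of men affected. That gives 20 affected men, A = 180 and F = 200.

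| p_m | p_f | Present | Absent as planned | Gap (points) |
|---|---|---|---|---|
| 30% | 30% | 30% | 30% | 0 |
| 30% | 45% | 30% | (54 + 90) / 380 = 37.9% | +7.9 |
| 20% | 40% | 20% | (36 + 80) / 380 = 30.5% | +10.5 |
| 40% | 20% | 40% | (72 + 40) / 380 = 29.5% | −10.5 |

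**Step 2: how often the planned test would be falsely significant.** This is the exact rejection probability of the two-sided Fisher test at 0.05, found by enumerating the binomial outcomes, with 50% men and no association among men.

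Sex difference of 15 points (30% against 45%, in either direction), 5 to 10% of men affected:

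| Patients | As planned |
|---|---|
| 100 | 0 to 4.2% |
| 200 | 0.6 to 7.4% |
| 300 | 3.4 to 7.1% |
| 400 | 3.7 to 8.4% |

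Restricted to men, the same settings give 0 to 4.1%.

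Sex difference of 20 points (first figure: 20% in men and 40% in women; second: the reverse):

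| Patients | Affected men | As planned | Men only |
|---|---|---|---|
| 200 | 5 | 0.6% / 7.8% | 2.0% / 1.6% |
| 200 | 10 | 5.2% / 8.9% | 2.4% / 3.9% |
| 400 | 10 | 6.3% / 8.8% | 2.6% / 3.9% |
| 400 | 20 | 13.4% / 16.2% | 3.7% / 3.5% |

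With equal rates by sex (30% in both), 400 patients and 20 affected men, the figures are 4.2% as planned and 3.8% in men only.

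**Step 3: the descriptive rate.** Over all patients, the reported frequency is the male share times the frequency in men. At an assumed 40 to 60% men, 10% among men appears as 4 to 6%, and 5% as 2 to 3%.

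**The case against.** The strongest reply is that little depends on this. Tables 2.9 and 3.4 are one-way screens of 28 characteristics without multiplicity control, and no confirmatory conclusion rests on epididymitis. A significant result in Table 2.9 leads only to a descriptive breakdown. Sex is tested in the same tables, so a reader would see a sex difference. Other factors related to sex may be confounded in the same way, and a filter on one of them does not supply the missing adjusted analysis. With few affected men, a gap of 8 to 10 points would often be lost in noise.

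Most of this stands, and it limits the weight of the point. It does not remove it. For other factors confounding by sex is a possibility; here it is written into the definition of the groups, and a filter removes it completely.

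A reader might infer three stronger points that the SAP does not support:

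- **That the all-patient frequency in Table 1.12.1 is wrong.** It is a true description of the analysis set. Sex is shown in the same table, so the rate among men can be derived.
- **That Table 3.5.2 has the same coding.** The rule in section 10.1 applies at the start of treatment. Section 10.3 allows an unknown or undescribed class for symptom evaluations, whereas section 11 has two classes only, so the coding of women in that table is not settled.
- **That ulcer of vulva has the same fault.** It is one of the four main symptoms, and section 10.1 defines the complete type of the disease by all four. If it were a female-only item, no man could be of complete type. It most likely denotes genital ulcer in both sexes.

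**Conclusion.** The point holds for the epididymitis comparisons in Tables 2.9 and 3.4. As written, they set affected men against unaffected men plus all women, and nothing elsewhere in the SAP restricts or adjusts this.

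Whether the result is actually biased depends on a sex difference in reactions or response, which the document cannot show. Without one there is no bias. On the assumed inputs, false rejection is mostly between 0 and about 9%. It exceeds that only in the most unfavourable setting examined (400 patients, 20 affected men, a 20-point sex difference), at 13 to 16%. For a rare factor in exploratory tables this is a modest fault, worth correcting because the correction is simple. It does not call the rest of the factor analysis into question.

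**What to change.** In Tables 2.9 and 3.4, add a note that the epididymitis rates and Fisher's exact test are computed in male patients of the safety or efficacy set only, with women shown as not applicable and left out of both denominator and test. The not-applicable class should be stated explicitly. Coding women as unknown would remove them from the test under section 9.5, but section 9.2 would keep them in the denominator of the rate.

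Optionally, give the epididymitis frequency in Tables 1.12.1 and 3.5.2 over male patients as well, following the precedent of pregnancy/lactation over female patients.

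The cost is one note and a sex filter per table, with no new data. The comparison has fewer patients, but those removed carry no information on this factor.

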**“2.9 incidence of adverse reactions by seriousness by patient characteristics”**

Patients included in analysis: Patients included in safety analysis

Objective of analysis: Based on test result described in 2.9, occurrence status of adverse reactions by patient characteristics with significant differences is shown by dividing them into serious and non-serious adverse reactions.

Analysis items: In adverse reactions that occurred in the period included in safety analysis, following items should be aggregated by patient characteristics and seriousness.

The number of patients, the number of patients in whom adverse reactions occurred, rate of patients in whom adverse reactions occurred, the number of adverse reactions, the number of patients in whom adverse reactions occurred and rate of these patients to those included in analysis by types of the reactions (SOC, PT) should be calculated.

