### 4. Outline of survey

#### 4.1. Objective of survey

Objective of this survey is to understand following matters when HUMIRA® subcutaneous injection (hereinafter referred to as “this drug”) is used in patients with gastro-intestinal Behcet disease.

- 1) Unknown adverse reactions (especially important adverse reactions)
- 2) Occurrence status of adverse reactions under actual use conditions
- 3) Factors that may contribute to safety and efficacy

<<Primary survey items>>

Infection, tuberculosis, interstitial pneumonia, malignant tumour, cardiac failure congestive, pancytopenia, autoimmune disease, demyelinating disorder, and administration site reaction

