### 9.5. Test method

Unknown or not described classification should not be included in test. In addition, test of data by classification is performed, the first hierarchy should be tested in principle. Multiplicity should not be considered.

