## 9.6. Level of significance

In principle, level of significance should be 5% on both sides.  $p<0.05$  (less than 5%) should be considered significant.

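### The by-seriousness breakdown in the second Table 2.9 depends on a test of all adverse reactions, so a factor that acts mainly on serious reactions can easily miss it

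*SAP*

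**What the plan says.** The relevant text is in SAP section 13.2, where two consecutive tables carry the number 2.9.

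- **First Table 2.9** lists 28 patient characteristics. For each it asks for "the number of patients with serious adverse reactions, and rate of these patients to those included in analysis", and the same for all adverse reactions. It then names one "test provided for the adverse reactions": Fisher's exact test for nominal factors, Mann-Whitney for ordinal ones. No test on serious reactions is named.
- **Second Table 2.9** gives the serious/non-serious split by SOC and PT, restricted as follows: "Based on test result described in 2.9, occurrence status of adverse reactions by patient characteristics with significant differences is shown".
- **Section 9.6** says that the "level of significance should be 5% on both sides" and that p below 0.05 "should be considered significant". **Section 9.5** adds: "Multiplicity should not be considered".
- **Tables 2.13.1, 2.13.5, 2.14.1 and 2.16.1** give by-seriousness breakdowns for hepatic function disorder, central nervous lesion, renal impairment and elderly patients, whatever any test shows.
- **Section 4.1** names as the third objective: "Factors that may contribute to safety and efficacy".

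**The concern.** The test that opens the detailed table does not match what the table shows. The table separates serious from non-serious reactions, but a factor reaches it only through a test that pools them. If a factor raises serious reactions and leaves the more frequent non-serious ones unchanged, the pooled difference is smaller than the serious one and sits on a higher, noisier background rate. The test then has little power for the kind of factor the table would be most useful for.

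Four of the 28 characteristics escape the gate through their own tables. The other 24 depend on it, among them previous infliximab, concomitant oral steroid and mean daily dose. When such a factor is not significant on all reactions, its breakdown by seriousness, SOC and PT is not produced. No factor, gated or not, has a test on serious reactions. Finding factors that contribute to safety is a stated objective, so this screening step matters.

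**Working it through.** The SAP gives no power statement or expected rate, and section 4.3 leaves the number of patients undecided, so there is no planned figure to reproduce. All rates and sample sizes below are assumptions.

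**Inputs**
- From the SAP: two-sided 5% level; Fisher's exact test for nominal factors; no multiplicity adjustment.
- Assumed: serious-reaction rate s without the factor and 3s with it; probability q of a non-serious reaction, the same in both groups and independent of serious reactions; a binary factor; N = 100 to 500.

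**Dilution.** P(any reaction) = 1 − (1 − serious rate)(1 − q). With s = 5% and q = 25%:
- without the factor: 1 − 0.95 × 0.75 = 0.2875
- with the factor: 1 − 0.85 × 0.75 = 0.3625

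A threefold contrast in serious reactions (5% v 15%, a 10-point difference) becomes 28.8% v 36.3%, a 7.5-point difference on a much higher base rate.

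**Power.** Exact two-sided Fisher power by full enumeration, with 20% of patients having the factor:

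| N (with / without factor) | Gate: all reactions, 36.3% v 28.8% | Direct: serious reactions, 15% v 5% |
|---|---|---|
| 100 (20 / 80) | 7.9% | 29.8% |
| 200 (40 / 160) | 13.4% | 52.3% |
| 300 (60 / 240) | 19.2% | 66.8% |
| 500 (100 / 400) | 29.0% | 87.2% |

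**Sensitivity to the rates.** The grid was s = 3%, 5%, 10%; q = 15%, 25%, 40%; factor prevalence 10%, 20%, 50%; N = 100, 200, 300, 400, 500. That is 3 × 3 × 3 × 5 = 135 scenarios, 45 for each s.

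| Serious rate (without v with) | Range of probability of passing the gate | Scenarios at 50% or more |
|---|---|---|
| 3% v 9% | 0.04 to 0.26 | 0 of 45 |
| 5% v 15% | 0.06 to 0.57 | 1 of 45 |
| 10% v 30% | 0.10 to 0.98 | 22 of 45 |

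The factor misses the gate more often than not in 135 − 23 = 112 scenarios.

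**Where the gate does better**
- *Higher serious rates.* With 10% v 30% and q = 25%, any-reaction rates are 1 − 0.90 × 0.75 = 32.5% and 1 − 0.70 × 0.75 = 47.5%. At 20% prevalence the gate passes the factor in 55% (N = 300) and 78% (N = 500). At 50% prevalence it passes in 73% and 92%.
- *Non-serious reactions also rise.* With serious 5% v 15% and non-serious 25% v 40%, the any-reaction rate with the factor is 1 − 0.85 × 0.60 = 49%, against 28.75%. At 20% prevalence the gate passes the factor in 34%, 64%, 82% and 96% at N = 100, 200, 300 and 500. The direct serious test gives 30%, 52%, 67% and 87%, so here the gate is the more powerful of the two.

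Ordinal factors, tested by Mann-Whitney, were not computed.

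**The case against.** Four points can be made for the plan.

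**Serious reactions are not hidden.** A reader might infer that a non-significant factor is treated as showing no difference, or that its serious reactions are never listed. The SAP supports neither. The first Table 2.9 prints serious counts and rates for every factor, so a 5% v 15% contrast would be visible. Table 2.17 lists serious reactions by SOC and PT for all safety patients, and Table 1.4 lists events with their seriousness patient by patient, beside many of the characteristics. This stands. The loss is confined to the aggregated SOC/PT breakdown by factor and seriousness, and to a test on serious reactions.

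**The tested endpoint matches the planned item.** Section 5.1 asks for the incidence of adverse reactions by patient characteristics, and in section 4.1 the emphasis on important reactions belongs to the first objective, on unknown reactions. That is fair, and it justifies testing all reactions. It does not justify using that test alone to decide which factors are broken down by seriousness.

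**The size depends on chosen rates.** A reader might infer that a factor tripling serious reactions usually fails the gate. That holds over most of the grid at 3% to 5% baseline, but not at 10% v 30% with large N and a common factor, nor when non-serious reactions rise too. This also stands, and no general statement of frequency is made here.

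**More tests mean more false positives.** Adding 28 tests at 5%, if they were independent and of full size, would give a chance of at least one false positive of 1 − 0.95^28 = 76%. Fisher's test is conservative, so the true figure would be lower. The cost is real but acceptable for signal-finding, where the SAP already declines to adjust.

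**Conclusion.** The point holds in limited form. The SAP screens factors for a by-seriousness table with a test on all adverse reactions and tests serious reactions nowhere in Table 2.9. A factor acting mainly on serious reactions can easily miss the detailed table. In the main illustration it passes in about 8% to 29% of surveys at N = 100 to 500, against 30% to 87% for a direct test.

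Those figures rest on assumed rates (serious 5% v 15%, non-serious 25% in both groups, independent), a binary factor and 20% prevalence, none of which the SAP gives. If *the adverse reactions* in the first Table 2.9 was meant to cover both endpoints, the text does not say so, nor which p-value would then open the second table; the wording would still need correcting.

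This is a cheap improvement to an exploratory analysis. It does not invalidate the safety reporting.

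**What to change.** In section 13.2:

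1. In the first Table 2.9, apply the stated Fisher or Mann-Whitney test to serious adverse reactions as well as to all adverse reactions.
2. For every factor, print an effect estimate (rate difference or odds ratio) with a 95% confidence interval for both endpoints, and say that a non-significant factor is to be read from its interval.
3. Produce the second Table 2.9 whenever either endpoint is significant, or for all factors. Keeping the all-reaction test as one of the two triggers retains its advantage when both kinds of reaction rise.
4. State that these tests are exploratory, unadjusted and meant for signal-finding.

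The cost is a change of SAP wording, a longer table set and more unadjusted tests to read. The serious-reaction counts are already in the table, so no new data are needed. The added test is no guarantee in a small survey: in the main illustration it still misses about 70% at N = 100 and 48% at N = 200, which is why the confidence intervals should be printed as well.
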